Sasso and colleagues retrospectively reviewed their experience with selective nerve blocks in predicting surgical outcome for lumbar and cervical radiculopathy. The authors reviewed 101 patients all, which underwent cervical or lumbar decompression. The injection technique was standardized for both the cervical and lumbar regions. A positive injection was determined if there was an immediate >95% relief of pain and VAS score of 0-1. The overall predictive value of SNRB was 91% while the negative predictive value was 40%²¹. Williams and Germon recently reported on their experience with SNRB in 100 consecutive patients. This retrospective review included patients who presented with diagnostic uncertainty based on history, physical exam and imaging as to whether nerve root compression was responsible for their symptoms. All patients had imaging demonstration of either foraminal or lateral recess stenosis. All patients underwent a standardized injection performed by the same operator. A standardized approach to a positive or negative injection was utilized. Specifically, the injection to be effective result in 1) initial reproduction of the patient's typical radicular pain, 2) an initial radiculogram, 3) an appropriate motor and sensory disturbance immediately after blockade and 4) and whether good pain relief during activity was present during presence of blockade. In patients who's symptoms did not improve 3 months after surgery, an MRI was ordered. Fifty-one patients underwent decompression surgery after a successful SNRB; 41 patients had a good outcome after surgery, while 10 did not. Nine patients who did not have relief of their pain still underwent decompression surgery; 6 of these patients had relief of their symptoms, 2 did not improve and one was lost to follow-up. The positive predictive value was found to be 80.4%; while the

negative predictive value was 22.2%. The resultant sensitivity was 85.4% and specificity 16.7%²⁶.

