Both Sasso et al. and Williams and Germon studies are limited by their retrospective design. Bias regarding patients chosen for surgery, type of surgery performed and ultimate outcome cannot be minimized or mitigated. Patients included were not homogeneous, especially in Sasso et al, where cervical patients were included. Validated patient reported outcome measures were not utilized, which negatively impacts the true definition of outcome following surgery and overall predictive value of SRNB. Most importantly, the threshold for a positive response was determined and set *a priori* in both studies. A dichotomous positive or negative response to injection was utilized and is likely overly simplistic. As stated by the authors, the threshold for a positive response may have been set too high and this could have explained the low negative predictive value of SNRB reported. Lastly, the sample size in both studies was too small to make subgroup analysis and determine which aspects of the response to the SNRB predict a good surgical outcome.

There is currently no agreed upon gold standard against which to make comparisons of accuracy of SNRB. Some have defined accuracy based on demonstration of epidural spread of contrast along the nerve of interest²⁷, anatomic studies¹⁵, changes in physiology²², or compared to EMG or myelography¹⁰. Moreover, there is no agreed upon standardized needle placement for SNRB. The needle may be placed classically at the superior anterior foramen, alternatively, the needle may be placed in Kambin's triangle. Both target the nerve in the foramen, but at differing anatomic positions. An injection in either place should block the desired nerve, but in differing anatomic locations and potentially resulting in a varying diagnostic response. Many consider a transforaminal epidural steroid injection diagnostic, yet this injection involves epidural placement of drug and steroid and thus is not diagnostic. Lastly, there is no standard as to what medication or cocktail of medication and volume should be injected. Differing volumes and concentration of anesthetic injected will obviously have a variable impact on diagnostic accuracy.

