SNRB are technically difficult and the ability to selectively anesthetize a single nerve root has been questioned. The more recent studies attempt to circumvent this issue artificially by application of contemporaneous imaging to confirm SNRB placement in the correct location^{26, 28}. Evidence suggests that compression of the dorsal root ganglion is more predictive of radicular symptoms as compared to a more central region of compression^{8, 18}. Ideally, the target of "block" should be the DRG. There is known variation in the location of DRG in foramen, it may be located intraforaminally, extraforaminally, or intraspinally¹⁵. In order to account for this, some studies have used electrostimulation in addition to fluoroscopy²⁷. This variability has impact on the diagnostic yield of SNRB.

Another issue with SNRB is the lack of consensus on what constitutes a “positive” response. Some use a dichotomous approach with any improvement in pain used as a positive response, while others document an *a priori* level of pain improvement as a determination of “positive”. Some use an arbitrary cut-off in pain reduction; 50%, 80% or a two-point reduction in the visual analog pain scale²². If the cut-off is not met, the nerve is determined to not be the pain generator. This arbitrary approach may have a significant impact on determination of diagnostic accuracy. Patient expectations and placebo may also have an impact on diagnostic results. The impact is unknown but must be minimized or at least realized when utilizing SNRB. “Blinding” the patient to the procedure and a standardized informed consent and pre- and intraprocedural flow should minimize impact.

The view that a dichotomous response (positive vs. negative) to SNRB is overly simplistic. It is likely that there is a threshold of response, which predicts improving outcomes. It may be that as the degree of pain or functional improvement following injection will have a greater predictive value. Moreover, improvement on some aspects of the injection but not all may still predict a good outcome (i.e., motor and sensory changes in the nerve of interest but no significant improvement in pain). Knowledge of such a diagnostic threshold will help plan ultimate surgical or non-surgical treatment.

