To improve the diagnostic value of SNRB, a threshold between positive and negative responses will be set that is best able to predict whether a patient will have a good surgical outcome. To measure the response to injection, post-injection VAS pain scores and functional assessments will be compared to pre-injection values for each patient.

First, the functional and VAS pain measures of improvement will be analyzed individually. A positive functional response to injection will be defined by setting thresholds in the timed 30-meter walk test that best differentiates patients who respond to surgery from those who do not. The accuracy of the test will be defined by its sensitivity and specificity and by its negative and positive predictive values. Separately, a threshold defining a positive response to injection will be set using VAS leg pain improvements over pre-injection values.

Then, a logistic regression analysis will be performed, including pain assessments and walk test improvements as predictors. This model will assign a value between 0 and 1 that represents how likely it is that a patient who responds to SNRB with some amount of reduction in leg pain and improvement in

[name]

Threshold Response of Selective Nerve Root Block

functional ability has a good surgical outcome. A threshold in the model's predictive values will be set to define a positive response to the injection. This will again be done to maximize its diagnostic accuracy with respect to sensitivity and specificity and to positive and negative predictive values.

Positive and negative predictive values and their 95% confidence intervals will be reported both for the individual analyses and for the combined logistic regression analysis. Lastly, variable selection will be performed in an attempt to simplify the logistic regression model.

Due to the fact that a threshold response to SNRB has not been studied, we are not able to perform an adequate power analysis. We will use the data from this pilot study to perform a power analysis for a planned larger randomized trial. To have an adequate sample yet complete the study in a 12 month time period we plan to enroll 50 patients.

Plans for Dissemination of Results

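### Aim 1 has no predictive value at a cut-off fixed in advance: PPV and NPV are planned only at thresholds chosen from the same 50 patients

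*Combined protocol and SAP*

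**What the plan says.** Specific Aims separates two tasks. Aim 1 is to determine the PPV and NPV of the block prospectively. Aim 2 is to find the threshold of response that predicts a good result.

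The Statistical Analysis section does not keep them apart. It sets a walk-test threshold to separate surgical responders from non-responders. For pain it says: "Separately, a threshold defining a positive response to injection will be set using VAS leg pain improvements over pre-injection values". It then sets a third threshold on the predicted probability from a logistic model. PPV and NPV with 95% confidence intervals are reported for these individual and combined analyses only. No correction for choosing the threshold on the same patients is described. The planned sample is 50, with no power calculation.

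The Background names several cut-offs already in use. For the 101-patient retrospective study: "A positive injection was determined if there was an immediate >95% relief of pain and VAS score of 0-1". More generally: "Some use an arbitrary cut-off in pain reduction; 50%, 80% or a two-point reduction in the visual analog pain scale". It also reports, as the cited authors' own view, that "the threshold for a positive response may have been set too high and this could have explained the low negative predictive value of SNRB reported". None of these cut-offs reappears in the analysis plan.

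**The concern.** A predictive value estimated at the cut-off that best separates the same patients is biased upwards. If that is the only kind reported, Aim 1 has no estimate free of this bias.

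The Background makes a low published NPV, and the level of the cut-off, part of the motivation for the study. An NPV above the published 22.2% or 40% will invite the conclusion that a better threshold has been found. The planned analysis cannot separate that from the gain that selection produces by itself.

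The remedy is available within the design. VAS leg pain is recorded before and after the injection, and every enrolled patient is to have surgery whatever the response. PPV and NPV at any fixed VAS cut-off can therefore be estimated in one cohort, without test-negative patients being withheld from surgery.

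**Working it through.** **1. Reproduce the published figures.** The Background gives counts for the 100-patient study. For test-positives: "Fifty-one patients underwent decompression surgery after a successful SNRB; 41 patients had a good outcome after surgery, while 10 did not". Of nine test-negatives operated on, 6 were relieved, 2 were not and 1 was lost to follow-up.

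- PPV = 41/51 = 80.4% (exact 95% CI 66.9% to 90.2%)
- NPV = 2/9 = 22.2% (2.8% to 60.0%)
- Sensitivity = 41/48 = 85.4%
- Specificity = 2/12 = 16.7% (2.1% to 48.4%)

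All four match the protocol, provided the lost patient is counted as a test-negative with a good outcome. Without that patient, NPV is 2/8 = 25.0%. The 91%/40% of the 101-patient study cannot be reproduced because no counts are given.

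**2. What a useless test would give.** On the same counting, 48/60 = 80% had a good outcome. A test unrelated to outcome has NPV = 1 − success rate = 12/60 = 20%. The published 22.2% is almost the same, so it fits an uninformative test as well as a cut-off set too high.

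**3. What choosing the cut-off adds.** This was simulated for 50 patients, with the cut-off maximising sensitivity + specificity − 1 (Youden). The plan names no criterion, so Youden is an assumption, as are the success rates and the signal sizes. True NPV is the NPV of the chosen cut-off in new patients.

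| Success rate | Signal | Mean apparent NPV | True NPV | Excess |
|---|---|---|---|---|
| 60% | none | 0.53 | 0.40 | 0.13 |
| 70% | none | 0.43 | 0.30 | 0.13 |
| 80% | none | 0.32 | 0.20 | 0.12 |
| 80% | 0.5 SD | 0.39 | 0.28 | 0.11 |
| 80% | 1 SD | 0.46 | 0.37 | 0.09 |

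The 70% row was re-run with normal and with beta-distributed responses and gave about 0.43 each time. In the same setting, a cut-off fixed at 50% relief averaged 0.30, which is unbiased. PPV is inflated too: 0.89 against 0.80 at 80% success with no signal. The combined logistic model, fitted and cut on the same patients, was not simulated.

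**4. What the fixed cut-offs could show at N = 50.** The documents do not say how many patients will be negative at a given cut-off, so a range is assumed. Exact 95% intervals for NPV:

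- 8 negatives: 2/8 = 25% (3% to 65%); 3/8 = 38% (9% to 76%)
- 15 negatives: 3/15 = 20% (4% to 48%); 6/15 = 40% (16% to 68%)
- 25 negatives: 6/25 = 24% (9% to 45%); 10/25 = 40% (21% to 61%)

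**5. What comparing cut-offs could show.** Assume 70% success, three beta distributions of relief, and a log-odds slope of 1.5 to 3 over 0-100% relief. True NPV is then 31-32% at the 95% cut-off and 38-52% at the 50% cut-off, a rise of about 7 to 20 points. With no association it is 30% at both. At N = 50 the within-cohort difference has an SD of about 6 to 12 points. A bootstrap 95% CI for it lay above zero in about 14-23% of simulated trials at slope 1.5 and 38-58% at slope 3. With no association, a rise of 7 points or more still appeared in as many as 27% of trials.

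**The case against.** The best defence is that this is a 50-patient pilot meant to find a threshold, not to replicate old ones, and that the raw VAS data would let anyone apply another cut-off later. Several parts of that defence stand.

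- A reader might infer that the protocol attributes the low NPV to high cut-offs and then leaves its central explanation untested. The documents do not support this. The remark is hedged and credited to the cited authors, other sections list several further causes of disagreement, and neither aim is to explain earlier NPVs.
- A reader might infer that the plan cannot show whether relief predicts outcome at all. The planned logistic regression on pain and walk-test change addresses that association directly. A rise in NPV at lower cut-offs would mainly restate it.
- A reader might infer that a table at published cut-offs would confirm or refute the explanation. Step 5 shows it would not: a flat result at N = 50 proves nothing, and a rise can be chance.
- A reader might infer that the table would make the results directly comparable with 91%/40% and 80.4%/22.2%. It would not. This trial uses a multi-component outcome, whereas the protocol says the earlier studies used no validated patient-reported measures. One of them included cervical cases. The other used a four-part rule whose pain element, "whether good pain relief during activity was present during presence of blockade", has no number. Equally, the comparison is unplanned rather than impossible, since the VAS data are collected.

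One part of the defence fails. Cut-offs picked after the data are seen do not give Aim 1 a definition fixed in advance, and pilot status does not remove the optimism. The protocol intends these data to shape the threshold and the power calculation of the larger study, so inflated values would carry forward.

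**Conclusion.** The point holds in a limited form. Every planned PPV and NPV sits at a threshold chosen from the same 50 patients, so Aim 1 has no estimate at a prespecified definition, and none of the cut-offs the protocol cites is analysed. With no signal, the optimised NPV would overstate the truth by about 12 to 13 points on average (0.43 against 0.30 at 70% success). That is enough to exceed the published 22.2% or 40% by selection alone. The size rests on assumed success rates, an assumed Youden criterion and 50 analysable patients.

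It goes no further than that. The plan is not shown to be wrong about why earlier NPVs were low, and the missing analysis would not decide that question. The gap is secondary, but it is worth closing because doing so costs almost nothing.

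**What to change.** Add to the Statistical Analysis section, under Aim 1, one prespecified table of PPV, NPV, sensitivity and specificity with exact 95% confidence intervals at four VAS leg-pain cut-offs:

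- more than 95% relief with post-injection VAS 0-1
- at least 80% relief
- at least 50% relief
- a reduction of at least 2 VAS points

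Name the post-injection score to be used, since VAS is recorded after recovery, after the walk test and at 48 hours. Use the same surgical outcome as the main analysis. Eligibility sets no minimum leg pain, so also state how a patient with pre-injection VAS below 2 is classified. Keep the data-derived thresholds under Aim 2.

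State in the plan that the table is descriptive. Intervals will be wide: on the assumptions in step 4, NPV intervals span about 36 to 67 points. The table cannot by itself confirm or refute the view that earlier thresholds were too high. Comparison with the published figures stays limited by the different outcome definitions, the cervical cases in one study and the non-numeric four-part rule in the other.

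The cost is one extra table with wide intervals. No new data, visits or patients are needed.

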Aim 1: Prospectively determine the positive and negative predictive value of SNRB in the surgical treatment of lumbar foraminal stenosis. Prior to a single level foraminotomy for lumbar foraminal stenosis patients will undergo SNRB of the suspected nerve root. All enrolled patients will proceed to surgery despite the response to injection. All injections will be performed in a standard format-utilizing anesthetic only and under fluoroscopic guidance. All patients will complete an ambulation assessment immediately before and following the injection. Distance and time will be recorded. All injection patients will be called within 48 hours of the injection to determine response to the injection and recorded as Pre- and Post injection VAS leg as well as length of time of the response recorded in minutes. Patients will be seen at 6 weeks, 3 months and 12 months following surgery and outcome measured by VAS-leg, Oswestry Disability Index (ODI), Pain Disability Questionnaire (PDQ) and EQ-5D.

Aim 2: Determine the threshold of positive predictive response. The relationship between degree of pain improvement following SNRB and outcomes following surgery is currently unknown. Each patient will therefore report their change in leg pain before and after injection as well as the length of time of improvement. These data will be used to determine the optimal improvement in leg pain and duration of improvement, which predicts a statistical and meaningful improvement in leg pain following foramintomy.

Background and significance

Lumbar radiculopathy in the setting of degenerative disease is a common presenting symptom; its prevalence is estimated to be 2-5% of the US population. Although patients typically present with pain associated with one or multiple nerve roots, their MRI may demonstrate multi-level foraminal and/or

canal stenosis. Moreover, these degenerative findings seen on imaging are common in asymptomatic people. Several studies have found no correlation between MRI findings and clinical symptoms^{4, 16, 17, 25}. Others have shown that MRI evidence of stenosis increases with age despite absence of symptoms, noting that almost 20% of individuals >60 years of age and up to 80% of those >70 years of age have evidence of stenosis without clinical symptoms^{3, 20}.

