Following recovery of the injection, the patient will report a post-injection VAS leg pain score. The patient will then perform a post injection 30-meter walk test. Time and cadence count will be recorded as well as post walk test VAS leg pain. Patients will resume normal activities and given a pain diary.

4. 48 Hour Post Injection Assessment

At 48 hours post injection, all patients will be called. A 48-hour VAS leg pain will be assessed and pain diary reviewed. The duration of pain

change will be recorded. The change will be based on the minutes elapsed since pain improved post injection and the number of hours it took to return back to baseline.

5. Lumbar Foraminotomy

All operations will be performed at the main campus Cleveland Clinic by a fellowship trained spine surgeon. After induction of general anesthesia and patient positioning, the lumbar skin will be prepped and draped per hospital protocol. A preoperative lateral radiograph will confirm the level of incision. The smallest incision possible will be made and subperiosteal exposure utilized to expose the level of foraminotomy. The spinous process is next resected and a laminotomy performed on the index ipsilateral side. Following medial facetectomy, Kerrison Rongeurs will be utilized to remove overgrown bone and ligamentum flavum to decompress the neural foramen. Discectomy may be required to fully decompress the existing nerve root. The easy passage of a Woodson elevator through the foramen will be utilized to confirm adequate opening of the foramen.

6. Following surgery all patients will be seen at 6 weeks, 3, 6 and 12 months.

During follow-up, patient reported outcomes will be recorded including VAS leg, ODI, PDQ and EQ-5D. Any adverse events will be recorded and noted associated or not associated with the index operation. **Any patient without improvement in symptoms 3 months post surgery will undergo MRI to assess adequacy of foraminal decompression.**

7. An excellent surgical outcome will be defined as 15-point improvement in ODI, 26 point improvement in PDQ, improvement in VAS leg pain to 0-2, and improvement in quality of life per EQ5D.

Statistical Analysis

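### Must pre-injection VAS be a fixed term in the analysis that sets the VAS cut-off for a positive block?

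*Combined protocol and SAP*

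**What the plan says.** The Statistical Analysis section describes two kinds of analysis. In the first, each measure is taken alone, and for pain "a threshold defining a positive response to injection will be set using VAS leg pain improvements over pre-injection values". In the second, "a logistic regression analysis will be performed, including pain assessments and walk test improvements as predictors". The model's output is the chance of success for "a patient who responds to SNRB with some amount of reduction in leg pain" and with some gain in function. The plan then adds that "variable selection will be performed in an attempt to simplify the logistic regression model", naming no method and no protected term. "Positive and negative predictive values and their 95% confidence intervals will be reported both for the individual analyses" and also for the combined model.

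The threshold is meant to be the one "best able to predict whether a patient will have a good surgical outcome". Description of Procedures, item 7, gives the numerical definition: "An excellent surgical outcome will be defined as 15-point improvement in ODI, 26 point improvement in PDQ, improvement in VAS leg pain to 0-2", together with better quality of life on EQ-5D. Aim 2 speaks instead of a pain response "which predicts a statistical and meaningful improvement in leg pain following foramintomy". Pre-injection VAS leg pain is recorded (Description of Procedures, item 1).

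**The concern.** Improvement from a starting value is tied to that value: a patient at VAS 4 cannot improve by more than 4 points. If starting pain also affects the surgical result, a cut-off in points may partly sort patients by how much pain they began with. Its predictive value would then be credited to the block. The section names no baseline term for the model, says nothing about keeping one through variable selection, and leaves points or percent open. The threshold is the pilot's main product, and Future Funding and Next Steps carries it into the design of a larger study, where starting pain may differ. Without a baseline-only comparison, a reader could not say what the block adds.

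**Working it through.** **The plan's own figure.** The only figure is the enrolment of 50. The plan says it was set by feasibility without a power analysis, so there is no calculation to reproduce. The documents give no VAS mean, SD or success rate, so every simulation input below is an assumption.

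**Step 1: the text.** In the logistic model, pain assessments are listed separately from walk test improvements. Items 1 and 3 of Description of Procedures use the word assessment for the pre-injection and post-injection scores. If both scores enter, then b1·pre + b2·post = (b1 + b2)·pre − b2·(pre − post), which is the same model as improvement plus baseline. The later reference to an amount of reduction weakens this reading but does not exclude it. Baseline is unspecified, not left out.

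**Step 2: direction.** To reach VAS 2, a patient starting at 4 needs 2 points and a patient starting at 8 needs 6. A 3-point gain is 3/4 = 75% relief from 4 but 3/8 = 37.5% from 8. High starting pain therefore makes the end-state criterion harder and a change criterion easier. Item 7 combines both types.

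To see the two effects apart, the block was made uninformative: VAS mean 6.5, clipped to 3–10; independent proportional relief, Beta(2, 1.5) for the block and Beta(2.5, 1.2) for surgery; 200,000 patients per scenario.

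| Starting SD | AUC in points, outcome VAS 0–2 only | AUC in points, outcome gain of 3 or more |
|---|---|---|
| 1.0 | 0.470 | 0.549 |
| 1.5 | 0.437 | 0.612 |
| 2.0 | 0.405 | 0.669 |

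The effects run in opposite directions. Percent improvement gives an AUC of about 0.50 throughout.

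**Step 3: the outcome the protocol defines.** A second model used starting VAS of mean/SD 6/2 or 7/1.5, clipped to 1–10. Relief was either proportional (Beta(1.2, 1) block, Beta(2, 0.9) surgery) or additive (mean/SD 3.3/2.2 and 4.3/2.2 points, bounded by 0 and starting VAS). Baseline ODI was 45/14 and PDQ 80/25, each correlated 0.5 with VAS. ODI and PDQ relief were Beta(2, 1.5) and EQ-5D improvement 84%, each with latent correlation 0.6 to surgical relief. Success meant meeting all four criteria.

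- Uninformative block, points, four criteria: AUC 0.495 to 0.51 over repeated runs.
- Uninformative block, Aim 2 read as a 3-point gain (a figure not in the documents), 3-point cut-off, success in positives v negatives: proportional relief 79% v 58% (6/2) and 83% v 77% (7/1.5); additive relief 72% v 62% and 72% v 72%. Within starting VAS 8, proportional relief: 87% v 87%.

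**Step 4: what a forced term does with 50 patients.** The simulated success rate of 28–42% gives 0.28 × 50 = 14 to 0.42 × 50 = 21 successes. Two terms leave 7 to 10.5 successes per term; three leave 4.7 to 7. Out-of-sample AUC for a predictive block (latent correlation 0.5), four criteria:

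| Scenario | Points alone | Points + start | Change | Percent alone | Percent + start | Change |
|---|---|---|---|---|---|---|
| Proportional 6/2 | 0.655 | 0.665 | +0.010 | 0.689 | 0.672 | −0.017 |
| Proportional 7/1.5 | 0.681 | 0.679 | −0.002 | 0.694 | 0.679 | −0.015 |
| Additive 6/2 | 0.658 | 0.705 | +0.047 | 0.697 | 0.688 | −0.009 |
| Additive 7/1.5 | 0.687 | 0.721 | +0.034 | 0.721 | 0.716 | −0.005 |

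The points columns come from 2,000 trials of 50 and the percent columns from 600. Percent alone beats points plus starting VAS in both proportional cases and is within 0.008 of it in both additive cases.

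**Step 5: the stand-alone cut-off.** It is a single-measure threshold with no model behind it. A term added to the logistic model leaves it, its PPV and its NPV unchanged.

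**Step 6: one pooled cut-off at different starting pain.** For starting VAS 4 v 8, PPV was 59% v 51% (6/2) and 49% v 53% (7/1.5) under proportional relief, and 53% v 31% and 41% v 33% under additive relief. The gaps are 8, −4, 22 and 8 points. The 95% interval for PPV with 50 patients is 34–37 points wide overall and 42–56 within halves of starting VAS. At 7/1.5, only about 4% of patients lie within half a point of VAS 4, or 0.04 × 50 = 2 patients.

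**The case for a change.** The strongest case for acting is that the conditions that decide whether mixing occurs are the ones left open. If the analyst counts points and takes Aim 2 literally, an uninformative block can show a gap of 79 − 58 = 21 percentage points that comes from starting pain. If relief is additive and counted in points, forcing the baseline in gains 0.034 to 0.047 in AUC, yet backward elimination at p<0.05 would drop it in 57–63% of trials. Percent is not a perfect escape: under additive relief at 6/2, an uninformative block with a 50% cut-off shows 37% v 31% on the four criteria and 65% v 71% on Aim 2. The change would also be wording only, because the score is already collected.

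The conditional part of this stands: in points, with a change-in-pain outcome, starting pain can pass for block response. It does not support a fixed term whatever the scale, because that costs accuracy on the percent scale in all four scenarios and gains nothing dependable in points under proportional relief. A baseline-only comparison would be informative, but it answers a different question from Aim 1, which asks for PPV and NPV. Those remain valid descriptions of this cohort at its own mix of starting pain.

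**Conclusion.** No change to the plan follows. Part of the point is missing detail that an analyst fills sensibly when setting up the analysis: points or percent, which outcome the threshold predicts, and which scores count as pain assessments. The rest is a fair trade-off. Under the four-part outcome the false signal from starting pain is close to nil (AUC 0.495 to 0.51). A forced term changes out-of-sample AUC by between −0.017 and +0.047 depending on scale and on how relief works, at the price of one more parameter on about 14 to 21 successes. It leaves the stand-alone VAS cut-off as it is. A baseline-only model may be shown beside the planned PPV and NPV as exploratory, and would alter neither.

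All sizes rest on assumed VAS, ODI, PDQ and relief distributions, since the documents supply none. The conclusion is weakest if improvement is counted in points and success is judged by leg pain change alone.
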